#### **Appendix 4. Example SAS code for Delayed Entry Model in Survival Analysis**

Delayed entry model in survival analysis:

The total survival time is the length of time specified by the **time** variable. Entry into Study Fx1B-201 is after the amount of time specified by the **los** variable, which is defined from symptom onset to the start of Fx1B-201. The amount of time that the subjects were at risk in this model is **time - los**.

```
proc phreg data=data; /* add the METHOD=PL option in the baseline
statement only when using SAS version 9.2 or higher */
  model time*deathflag(0)= /entry=los;
  baseline out=table survival=S stderr=stderr atrisk=atrisk /method=pl ;
```

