The primary purpose of a therapy such as tafamidis is to stabilize the TTR tetramer, thus inhibiting the amyloid cascade and ultimately halting or slowing TTR-FAP disease progression over a sustained period of time. During the 18-month period of intervention in Study Fx-005, tafamidis slowed the course of neurological impairment and maintained quality of life in treated patients. Together, with the extension Study Fx-006 data, tafamidis demonstrated a sustained effect over 30 months, a period of time representing approximately 25% of the average TTR-FAPPN disease duration of 10 years. Further, Study Fx1A-201 was a small Phase 2II open label, single-treatment arm study designed primarily to determine the efficacy of tafamidis in stabilizing TTR variants other than the V30M (valine replaced by methionine at position 30) mutation. The results from this study of non-V30M TTR-FAP patients, which represented an older, more severely affected patient population, strongly supported the observed efficacy of tafamidis in V30M patients. As in Study Fx-005, the consistency of response across endpoints measuring different aspects of this multi-faceted disease was again observed following 12 months treatment with tafamidis. The results indicated the disease-modifying utility of tafamidis in treating all patients with TTR-FAPPN, regardless of mutation.

Study Fx1B-201 was a small Phase 2 study in TTR-CM in which a total of 35 patients were enrolled and analyzed, 31 patients with wild-type genotype and 4 with V122I genotype. As expected, the patients were elderly (mean age approximately 76 years), with significant disease duration (approximately 8 years) and signs and symptoms of mild to moderate cardiac dysfunction (84% with NYHA Class I or II) at the time of enrollment.

Tafamidis effectively stabilized TTR in 34 of 35 (97.1%) patients, representing both wild-type and V122I, at Week 6, with approximately 88% stabilized throughout the 12 months.

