9.1. Sample Size Determination

There is no formal sample size calculation for this protocol. Subjects who completed Protocol Fx1B-201 are eligible; up to 35 subjects are expected to enroll in Protocol Fx1B-303.

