#### 8.1.3. Analyses for Time to Event Endpoints

Kaplan-Meier estimates will be computed for all time to event endpoints, including median and interquartile ranges, where appropriate. 95% confidence intervals will be presented at yearly intervals from the start of the investigational drug (baseline of Fx1B-201). Time to event will use randomization and onset of disease as starting points for the calculation of time to event.

Subjects are required to survive to enroll in the parent study (Fx1B-201). Such conditions yield a left-truncated death time distribution from symptom onset. To account for the potential immortal time bias, the time to death from onset of symptom will be analyzed using the delayed entry (left truncation) technique. Survival probabilities will be calculated conditional on subjects having survived until study entry of the parent study (Fx1B-201). SAS codes for the delayed entry (left truncation) technique are provided in Appendix 5.

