## 8.3. Safety Analyses

Safety data will be summarized for the safety analysis population.

**Treatment and Disposition of Subjects:** Subject evaluation groups will show end of study subject disposition and will show which subjects were analyzed for efficacy, as well as for

safety (adverse events and laboratory data). Frequency counts will be supplied for subject discontinuation(s) by treatment.

A listing of treatment duration for each subject will be reported in accordance with the sponsor reporting standards.

**Demographic and Baseline Characteristics.** A break-down of demographic data will be provided for age, race, weight, body mass index, and height. Each will be summarized by sex at birth and ‘All Subjects’ in accordance with the sponsor reporting standards. All baseline and disease characteristics will also be summarized for Fx1B-201 and B3461026, respectively.

**Discontinuations.** Subject discontinuations or temporary discontinuations due to adverse events will be detailed and summarized.

**Adverse events (AEs):** Adverse events will be summarized by causality and severity.

**Mortality and Hospitalization (all-cause and cardiac-related):** Time to all-cause mortality and time to cardiac-related mortality will be calculated from the first dose of the randomized treatment in Study Fx1B-201, and from onset of symptom, respectively. For cardiac-related mortality, subjects who died for reasons other than cardiovascular will be designated as censored at the time of death. Subjects alive at the end of the study will be censored at the last visit date. Death after discontinuation will be censored at time of discontinuation. For subjects who have received a liver and/or heart transplant, time will be censored at the time of transplant. The analyses will use the methods described for time to event endpoints in [Section 8.1.3](#). The analyses will be performed on the safety analysis population (defined in [Section 5.1](#)).

The number and percentage of subjects hospitalized (all-cause and cardiac-related) during the study will be summarized descriptively.

**Hematology, Biochemistry and Urinalysis:** Descriptive statistics will be provided for each test result and for change from baseline by visit.

Baseline is defined as the last evaluation prior to the first dose of study drug in Study Fx1B-201.

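### The delayed-entry survival curve from symptom onset starts with about one subject at risk, and no start time or minimum risk set is stated, so one early death can lower every later value

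*SAP*

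**What the plan says.** SAP 8.1.3 analyses time to death from symptom onset by delayed entry, to deal with immortal time before the parent study. It describes the conditioning as follows: "Survival probabilities will be calculated conditional on subjects having survived until study entry of the parent study (Fx1B-201").

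Appendix 4 gives the implementation. The entry variable `los` is the interval "which is defined from symptom onset to the start of Fx1B-201", and the model statement is "model time*deathflag(0)= /entry=los". The output statement is "baseline out=table survival=S stderr=stderr atrisk=atrisk /method=pl", that is, a product-limit estimate with the standard error and number at risk written to a dataset. The appendix adds: "The amount of time that the subjects were at risk in this model is" the total time minus `los`.

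SAP 8.3 applies the mortality analyses, from first dose and from symptom onset, to subjects enrolled and dosed in Fx1B-303: "The analyses will be performed on the safety analysis population". Protocol 9.1 says "up to 35 subjects are expected to enroll in Protocol Fx1B-303". Protocol 1.2.4 describes the parent-study patients as elderly, "with significant disease duration (approximately 8 years").

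Neither document gives a common starting time for the onset curve, a minimum risk set, or a rule for when the curve may be read.

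**The concern.** In an ordinary Kaplan-Meier curve the small risk sets lie at the right, where they disturb only the tail. Under left truncation they also lie at the left. Only subjects enrolled soon after onset can contribute there, and a death among them rescales everything that follows.

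The conditioning sentence in SAP 8.1.3 does not settle this. Entry times differ between subjects and no single time is named to condition on, so a reader cannot tell from the plan what the plotted probability is conditional on. Conditioning on entry addresses the truncation bias; it does nothing for the instability.

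At stake are the level of the onset curve and any median taken from it. Both could be governed by one subject with a short disease history. SAP 3.2 allows interim results to go to scientific meetings or to regulators. A start time chosen only after an early drop had been seen would be open to challenge.

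**Working it through.** The plan states no survival figure, event count or formal sample size for this analysis, so there is nothing to reproduce first.

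**Inputs from the documents**
- Number of subjects: at most 35 (Protocol 9.1). Two of 35 died in the 12-month parent study (Protocol 1.2.4), so 35 − 2 = 33 at most could go on.
- Centre of the onset-to-entry time: about 8 years (Protocol 1.2.4).
- Death-free first year: members must have completed Fx1B-201 (Protocol 4.1), so none can die within about 12 months of `los`.
- Death rates for orientation: 2/35 = 5.7% in a year gives −ln(1 − 2/35) = 0.059 per year. A median of 60 months (Protocol 1.2.2), treated as time from entry, gives ln 2 / 5 = 0.139 per year. The natural-history cohort's 0.03 per patient-month (Protocol 1.2) gives 0.36 per year.

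**Assumed, because the documents do not give them**
- Gamma entry times with mean 8 years and SD 4–6 years.
- Exponential hazard of 0.06–0.20 per year after the death-free year.
- Follow-up uniform on 4–9 years from parent-study entry.

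**Step 1: the estimator.** S(t) is the product, over death times u ≤ t, of 1 − d(u)/Y(u), where Y(u) counts subjects with `los` < u ≤ `time`. One death multiplies all later values by 1 − 1/Y:

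| At risk, Y | Factor |
|---|---|
| 1 | 0 |
| 2 | 0.50 |
| 3 | 0.67 |
| 5 | 0.80 |
| 10 | 0.90 |
| 33 | 0.97 |

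**Step 2: a worked case.** Take 31 subjects. The earliest enters 0.5 years after onset and dies at 2.0 years; the next enters at 2.5 years. The death comes 2.0 − 0.5 = 1.5 years after entry, so it is compatible with completing the parent study. At 2.0 years Y = 1, so S becomes 0 and stays there, although 30 subjects enter later. Had three been at risk, every later value would be capped at 0.67.

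**Step 3: how often, in the SAP's population.** With 33 subjects and the assumptions above, the product of (1 − 1/Y) over deaths before the risk set first reaches five gave:
- a reduction of at least 20% in about 6–22% of trials;
- a reduction of at least 50% in about 1–9%;
- zero in about 0–3%.

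**Step 4: sensitivity.** At 0.36 per year the first two ranges rise to 27–36% and 12–19%, and zero reaches at most 5%. A second simulation used 31 or 35 subjects, SDs of 3, 5 and 8 years, the three document-based hazards and 6 years of follow-up. It gave a 4–51% chance that the first death alone lowers the curve by at least 20%. It gave a 0–4% chance of reaching zero with at least half the subjects still under observation or yet to enter.

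**Step 5: the other curve.** From first dose in Fx1B-201 everyone is at risk at the outset, so one early death costs about 1/33 = 3%.

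**The case against.** The estimator is valid in principle, and the study is descriptive: SAP 4.1 and 4.2 set no hypotheses, and no decision depends on this curve. The protocol's only named Kaplan-Meier plot runs from the start of Fx1B-201; the onset analysis was added in the SAP, and Appendix 4 is headed as example code. That code already outputs the number at risk and the standard error, and the protocol promises individual listings, so an early death could be traced. All of this stands and limits the consequence. None of it supplies a start time or ties any action to a small risk set.

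The probabilities depend on the left tail of the entry times, for which the documents offer only an approximate centre. That stands too. The mechanism follows from the specified code; its frequency does not.

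A reader might infer that collapse to zero is a realistic prospect. Larger figures arise if deaths can occur straight after entry: zero early in 3–13% of trials and a loss of at least 20% in 20–54%. They do not describe this plan, because entry is set at the start of Fx1B-201 and membership requires completing it.

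A reader might also infer that the yearly survival figures are exposed. SAP 8.1.3 ties its yearly intervals to the start of drug, as does Protocol 9.2.8 for its 1- to 4-year rates. No yearly readout from onset is specified, and medians are to be given only where appropriate.

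Finally, a threshold of five does not fully meet a 20% standard, since a death with exactly five at risk costs 20%. Under the SAP population the first death after such a start still lowered the curve by at least 20% in 3–14% of simulated trials. That is a fair limit on the remedy.

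**Conclusion.** The point holds as a modest, inexpensive improvement to a supplementary descriptive curve. As specified, the onset curve starts with about one subject at risk, and a single early death can lower all of it and any median read from it. A material distortion is plausible and near-total loss uncommon, on the ranges in Step 3. Those ranges rest on the assumed gamma shape, SDs, hazards and follow-up, and should be read as illustrative until the observed onset-to-entry times are examined. The documents do not support saying that the curve is likely to reach zero, or that the trial's mortality results as a whole are unreliable.

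**What to change.** In SAP 8.1.3 and Appendix 4:
- Prespecify a start time t0 for the onset curve, for example the earliest time since onset with at least five subjects at risk, or a higher stated minimum. With ten, a death at the threshold costs 10% rather than 20%.
- Report S(t | alive at t0) for t > t0, with numbers at risk shown.
- List any deaths before t0 individually.

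The cost is a sentence or two of SAP text and one filter in the program. Follow-up before t0 drops out of the curve, and a higher minimum discards more of it. The cut-off is a convention and t0 depends on the observed risk sets, which is why the rule should be fixed in advance. Small risk sets in the right tail remain; the displayed numbers at risk would make them visible.
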